3.2 Schematic Diagram of Study Design

Figure 3-1 Schematic Diagram of Study Design

FUP=follow-up; V=visit

Figure 3-2 Timing of blood sample collection, apheresis and dosing

* **On Dosing visits**, blood sample collection, apheresis and dosing should be performed on the same day. Apheresis should only start after the blood sample was collected and should end just before study drug administration.

3.3 Primary Endpoints

The primary endpoint of this study is:

- Percent change in LDL-C from baseline to Day 150 (Part 1 of study)

3.4 Secondary Endpoints

[figure not shown]
The key secondary endpoints of this study are:

- Absolute change in LDL-C from baseline to Day 150
- Percentage change in Apo-B from baseline to Day 150.
- Percentage change in non-HDL-C from baseline to Day 150.
- Percentage change in total cholesterol from baseline to Day 150.
- Proportion of subjects in each group with $\geq 30\%$ LDL-C reduction from baseline at Day 150.

The other secondary endpoints of this study are:

- Percentage change and absolute change in LDL-C from baseline to each assessment time up to Day 720 (ie, Days 90, 150, 180, 270, 330, 450, 510, 630, 690, and 720)
- Percentage change and absolute change from baseline to Days 90, 150, 180, 330, 510, 690, and 720 in PCSK9
- Percentage change and absolute change from baseline to Days 150, 180, 330, 510, 690, and 720 in total cholesterol, Apo-B, and non-HDL-C for subjects receiving inclisiran
- Individual responsiveness of subjects defined as the number of subjects reaching on treatment LDL-C levels of <25 mg/dL, <50 mg/dL, <70 mg/dL, and <100 mg/dL at Days 150, 180, 330, 510, 690, and 720 including proportion of subjects in each group who attain global lipid targets for their indication
- Proportion of subjects in each group with greater or equal to 30% LDL-C reduction from baseline at Days 150, 180, 330, 510, 690, and 720

- Absolute change and percentage change in other lipids, lipoproteins, apolipoproteins, and PCSK9 from baseline at each subsequent visit to Day 720
- Safety and tolerability profile of inclisiran as measured by AEs, SAEs, vital signs, clinical laboratory values, ECG measurements and formation and subsequent characterization of anti-drug antibodies (ADA)

3.6 Measures to Minimize/Avoid Bias

3.6.1 Blinded Study

Part 1 of this study will employ double-blind technique with a placebo control. Randomization via automated interactive response technology (IRT) will be used to assign subject to blinded investigational product kits. In addition, investigational product will be dispensed and administered in a blinded syringe. Blinding will minimize bias based on subject selection, baseline characteristics, clinical endpoint and AE reporting. Specifics on how the blind for the investigational product is maintained are provided in [Section 5.5](#).

4 Subject Population

This will be a multicenter, international study in subjects with HoFH and elevated LDL-C despite maximum tolerated dose of LDL-C lowering therapies.

4.1 Number of Subjects

At least 45 subjects will be randomized 2:1 to inclisiran or placebo.

4.2 Inclusion Criteria

Subjects may be included in the study if they meet all of the following criteria:

1. Males and females, ≥ 18 years of age with a diagnosis of HoFH by genetic confirmation or a clinical diagnosis based on a history of an untreated LDL-C concentration >500 mg/dL (13 mmol/L) together with either xanthoma before 10 years of age or evidence of heterozygous familial hypercholesterolemia in both parents (see [Appendix A](#)).
2. Stable on a low-fat diet
3. Subjects on statins should be receiving a maximally tolerated dose. Maximum tolerated dose is defined as the maximum dose of statin that can be taken on a regular basis without intolerable adverse events. Intolerance to any dose of any statin must be documented as historical AEs attributed to the statin in question in the source documentation and on the Medical History page of the electronic case report form (eCRF) (see [Appendix B](#))
4. Subjects not receiving statins must have documented evidence of intolerance to at least two different statins (see [Appendix B](#))
5. Subjects on lipid-lower therapies (such as statin and/or ezetimibe) should be on a stable dose for ≥ 30 days before screening with no planned medication or dose change during study participation
6. Fasting central laboratory LDL-C concentration ≥ 130 mg/dL (3.4 mmol/L)
7. Triglyceride concentration <400 mg/dL (4.5 mmol/L)
8. No current or planned renal dialysis or renal transplantation
9. Subjects on a documented regimen of LDL or plasma apheresis will be allowed to continue the apheresis during the study, if needed. The apheresis schedule should be maintained as deemed necessary and dosing should be scheduled to be done after apheresis. Administration of study drug should always occur at least 2 days following apheresis. Note: after implementation of protocol amendment 1, administration of study drug must occur right after apheresis on the same day of the study visit or at least 2 weeks following the last apheresis (see [Figure 3-2](#)).
10. Subjects must be willing and able to give written informed consent before initiation of any study-related procedures. The subject should be willing to comply with all required study procedures
11. Willing to follow all study procedures including adherence to dietary guidelines, study visits, fasting blood draws, and compliance with study treatment regimens

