HoFH	homozygous familial hypercholesterolemia
HR	heart rate
hsCRP	high sensitivity C-reactive protein
IB	Investigator's Brochure
ICH	International Conference on Harmonisation of Technical Requirements for Registration of Pharmaceuticals
IDMC	Independent Data Monitoring Committee
IFN- γ	interferon-gamma
IL6	interleukin 6
INR	International normalized ratio
IRB	Institutional Review Board
IRT	Interactive Response Technology
ITT	intent-to-treat
IV	Intravenous
L	Liter(s)
LDL	low density lipoprotein
LDL-C	low density lipoprotein cholesterol
LDLR	low density lipoprotein receptor
Lp(a)	lipoprotein(a)
<hr/>	
MCH	mean cell hemoglobin
MCHC	mean corpuscular hemoglobin concentration
MCV	mean corpuscular volume
MDCO	The Medicines Company
MedDRA	Medical Dictionary for Regulatory Activities
mg	Milligram
MI	myocardial infarction
MITT	Modified intent-to-treat
mL	milliliter(s)
mmHg	millimeters of mercury
mmol	Millimole
MMRM	mixed-effect models for repeated measures
mRNA	messenger ribonucleic acid
NYHA	New York Heart Association
PCS	potentially clinical significant
PCSK9	proprotein convertase subtilisin/kexin type 9
PD	pharmacodynamic
PEF	peak expiratory flow
PK	pharmacokinetic
PMM	Pattern-Mixture Model

PT	prothrombin time
RISC	RNA-induced silencing complex
RNA	ribonucleic acid
RNAi	ribonucleic acid interference
SAE	serious adverse event
SAP	Statistical Analysis Plan
SC	Subcutaneous
SD	standard deviation
siRNA	small interfering ribonucleic acid
SUSAR	suspected unexpected serious adverse reaction
$t_{1/2}$	terminal half-life
TBIL	total bilirubin
TC	total cholesterol
TEAE	treatment emergent adverse event
TNF- α	tumor necrosis factor-alpha
TTR	target transthyretin
ULN	upper limit of normal
US	United States
VLDL-C	very low density lipoprotein cholesterol
WHO	World Health Organization

Amendment 1 (08-Oct-2020)

Amendment rationale

The first subject for this trial was randomized in Feb 2019 and enrollment was completed in Sep 2019 (with 56 subjects enrolled). Part 1 (double-blind phase) of the trial was completed on 02-Mar-2020, when the last subject completed the Day 180 visit and treatment allocation was unblinded. At time of this amendment, 51 subjects are still on study treatment.

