Section 1.2.1	Last sentence: Additional nonclinical studies are ongoing or planned.	Removed	Updated to reflect that there are no ongoing or planned nonclinical studies at this time. The results from all completed nonclinical studies are available in the latest Investigator Brochure.
Section 1.2.2.1	Last sentence: Additional clinical pharmacology studies are ongoing or planned.	Removed	Updated to reflect that there are no ongoing or planned clinical pharmacology studies at this time. The results from all completed clinical pharmacology studies are available in latest Investigator Brochure.
Section 1.2.2.3	Study ORION-2	Updated study results, and added MDCO and Novartis protocol numbers	ORION-2 has been completed; updated study results to reflect this status
Section 1.2.2.4	Study ORION-7	Updated study results, and added MDCO and Novartis protocol numbers	ORION-7 has been completed; updated study results to reflect this status
Section 1.3 Known potential risks and benefits	referred to IB version 10	Referred to current version of IB;	Ensures that investigators reviews information from most current version of Investigator's Brochure
Section 2.2 Secondary objectives	• Proportion of subjects with at least 20% LDL-C reduction from Day 1 over time	• Proportion of subjects with at least 30% LDL-C over time	To align with secondary objectives as described in the Statistical Analysis Plan (SAP) submitted to FDA on 9-Mar-2020.

Section	Original protocol	Amendment	Rationale for change
Section 3.1 Type/Design of Study;	The apheresis schedule should be maintained as deemed necessary and dosing and subsequent assessments for LDL-C and other lipids should be scheduled to be done after apheresis, using the same frequency/timing as done at baseline.	Removed and replaced by: The apheresis schedule should be maintained as deemed necessary, using approximately the same frequency/timing as done at baseline.	To ensure that LDL-C measurements are not confounded by apheresis, specific time windows and new timing between sample collection, apheresis and study drug administration were introduced.

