Section 3.2	done at baseline. For example, if baseline LDL-C was drawn 2 days after apheresis, subsequent measurement of LDL-C and other lipids should be taken 2 days after a subsequent apheresis. Administration of study drug should always occur at least 2 days following apheresis.	When apheresis is performed during a study visit (Dosing or Non-Dosing), blood samples for measurement of LDL-C, other lipids and laboratory assessments must be collected before the apheresis. When apheresis is performed during a Dosing Visit, dosing should occur just after completion of the apheresis. The next scheduled apheresis must not occur within 72 hours of injection of inclisiran. The subsequent study visit must occur at least 2 weeks after an apheresis was performed to ensure LDL-C levels measured during a study visit are not confounded by the apheresis (see Figure 3-2 for details). Figure 3-2 – added to Section 3.2	
Section 3.1 Type/Design of Study	Subjects who have completed the study to Day 720 will be given the opportunity to enroll into an open-label extension trial.	removed	As other alternative treatment options are available and there is no need to provide patients with additional open-label inclisiran.

Section	Original protocol	Amendment	Rationale for change
Section 3.4 Secondary Endpoints		Added additional secondary endpoints: 
• Percentage change in Apo-B from baseline to Day 150.• Percentage change in non-HDL-C from baseline to Day 150.• Percentage change in total cholesterol from baseline to Day 150.• Proportion of subjects in each group with ≥30% LDL-C reduction from baseline at Day 150.	To align with the Statistical Analysis Plan (SAP) submitted to FDA on 9-Mar-2020.
Section 4.2 Inclusion Criteria		Inclusion 9 Note: After implementation of protocol amendment 1, administration of study drug must either occur right after apheresis on the same day of the study visit or at least 2 weeks following the last apheresis (see Figure 3-2).	Added additional clarification on proposed new timing of apheresis after implementation of the protocol amendment to ensure that apheresis is not impacting drug levels and/or LDL-C measurements.

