Subjects on a documented regimen of LDL or plasma apheresis will be allowed to continue their same regimen during the study using approximately the same frequency/timing as done at baseline. When apheresis is performed on a study visit (Dosing or Non-Dosing), blood samples for measurement of LDL-C, other lipids and laboratory assessments must be collected before the apheresis. When apheresis is performed on a Dosing Visit, dosing must occur just after completion of the apheresis. The next scheduled apheresis must not occur within 72 hours of injection of inclisiran. The subsequent study visit must occur at least 2 weeks after an apheresis was performed to ensure LDL-C levels measured during a study visit are not confounded by the apheresis (see [Figure 3-2](#) for details).

[figure not shown]

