6.4 Randomization (Day 1)

Randomization should only occur once subject eligibility is confirmed and will be conducted via an automated IRT to assign subjects to investigational product. All treatment groups will be studied concurrently. At least 45 subjects are planned to be randomized 2:1 (inclisiran: placebo) for inclusion in the study.

The following procedures will be performed prior to the injection:

- Assessment of inclusion and exclusion criteria
- Pregnancy test (performed locally, prior to any dosing, using central laboratory supplies) (women of childbearing potential only)
- Randomization
- Neurological examination ([Appendix C](#))
- Vital signs: blood pressure and heart rate ([Section 7.1.3](#))
- Fasting lipid profile/biomarkers ([Section 7.2](#))
- Central clinical laboratory (full serum chemistry, hematology and coagulation) ([Section 7.1.7](#))
- Urinalysis (performed locally, using central laboratory supplies)
- Assessment of ADA ([Section 7.1.7.8](#))

The following procedures will be performed after the injection:

- Concomitant medications
- AE/SAE reporting

Investigational product (inclisiran or placebo) administration will occur at this visit for all subjects as per [Section 5.1.1](#) and the Pharmacy Manual.

Subjects must be observed in the clinic for at least 30 minutes after injection.

Should a subject develop signs or symptoms of anaphylaxis when investigational product is injected, the investigator will need to collect a blood sample for tryptase within 30 minutes of the onset of anaphylaxis (or as soon as logically possible).

If a local reaction around the injection site occurs that requires the subject to be seen between visits or if a reaction is noticeable on a subsequent visit, photographs of the injection site may be obtained if deemed necessary. Photographs should be submitted to the study inbox.

Detailed instructions for investigational product administration are found in the Pharmacy Manual.

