10.3.3 Analysis Windows and Baseline

The observational period for the study includes the screening period (Day -28 to Day -1), the treatment period (Day 1 to Day 690), and the EOS visit (Day 720±3 weeks). Any event occurring beyond the defined observational period, even if collected on the eCRF, will not be included in the planned statistical analysis. However, all data, including that reported after the defined observational period, will be included in the subject data listings.

Unless otherwise specified, for evaluations that are collected at multiple occasions prior to initiation of investigational product administration, the latest evaluation will be considered the "Baseline" evaluation for analysis.

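### In apheresis subjects whose Day 1 sample came less than 2 weeks after a session, the late open-label LDL-C reduction is understated, because Amendment 1 changed the sampling gap but not the baseline

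*Protocol*

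**What the plan says.** Criterion 9 in protocol Section 4.2 carries two dosing rules for subjects on LDL or plasma apheresis. The general rule reads: "Administration of study drug should always occur at least 2 days following apheresis". A note then sets a different rule for a later period: "after implementation of protocol amendment 1, administration of study drug must occur right after apheresis on the same day of the study visit", or else at least 2 weeks after the last session.

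Section 3.1 sets the matching rule for visits: "The subsequent study visit must occur at least 2 weeks after an apheresis was performed". The reason it gives is to keep apheresis from confounding the measured LDL-C. On a day with a session, blood is drawn first.

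Section 6.4 puts the fasting lipid sample on Day 1 under the line "The following procedures will be performed prior to the injection". Section 10.3.3 fixes the baseline: "for evaluations that are collected at multiple occasions prior to initiation of investigational product administration, the latest evaluation will be considered the" baseline value.

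The Amendment 1 rationale dates the study: "enrollment was completed in Sep 2019 (with 56 subjects enrolled"), Part 1 complete on 02-Mar-2020, and the amendment itself dated 08-Oct-2020.

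Section 3.4 lists percent and absolute change in LDL-C from baseline at each assessment to Day 720, the same for total cholesterol, Apo-B and non-HDL-C at fewer visits, and the proportion with a reduction of at least 30%. Section 10.4.3.2 plans descriptive summaries of these by treatment group in the ITT population. It does not separate apheresis subjects or the two sampling rules.

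**The concern.** A change from baseline is interpretable when both samples are taken under like conditions. The Amendment 1 table shows that the original protocol secured this by matching: "if baseline LDL-C was drawn 2 days after apheresis, subsequent measurement of LDL-C and other lipids should be taken 2 days after" a later session. That text is superseded. It is used here only as evidence of how the baselines were collected.

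The amendment replaced matching with a fixed minimum gap. Its rationale opens with the purpose: "To ensure that LDL-C measurements are not confounded by apheresis, specific time windows and new timing between sample collection, apheresis and study drug administration". By that standard, a baseline drawn 2 to 13 days after a session is confounded and a follow-up sample under the new rule is not. If the session lowered the baseline, the later reduction looks smaller than it is.

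The change in rule falls late in the open-label period, where durability of effect is read. In affected subjects the artefact would resemble loss of effect, and some true responders at the 30% threshold would be counted as non-responders. The Section 3.1 rule covers other lipids as well as LDL-C, so total cholesterol, non-HDL-C and Apo-B raise the same question.

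**Working it through.** The plan gives no figure of its own on this point. The check has three steps.

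**1. Which rule governed the baselines?** The first subject was randomised in February 2019 and enrolment closed in September 2019. The amendment came about a year later. Every Day 1 sample was therefore drawn when the 2-day minimum applied.

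**2. Which visits can fall under the new rule?**
- Last subject: Day 180 on 02-Mar-2020. From then to 08-Oct-2020 is 220 days, so 180 + 220 = Day 400. A subject randomised on 30-Sep-2019 would be at Day 375. Either way Day 330 is past and Day 450 is the next scheduled visit.
- First enrollees: randomisation on 1 to 28 February 2019 gives Day 616 to Day 589 on 08-Oct-2020. The next scheduled visit is Day 630, which is 14 to 41 days away.

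At most five visits (Days 450, 510, 630, 690, 720) are affected for the last subjects, and three (Days 630, 690, 720) for the first. These are ceilings. The amendment needs ethics committee and health authority approval before a site may apply it, and visit windows are ignored here. Day 150 and Day 180 were complete in all subjects.

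**3. How large is the distortion?** Let p be the true fractional reduction. Let r be the fraction by which the Day 1 value lies below what the same subject would have shown at least 2 weeks after a session. Then

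measured change = (1 - p)/(1 - r) - 1.

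The value p = 0.20 is the effect assumed in Section 10.1. The values of r are assumptions, because the protocol gives none.

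| r | Measured change | Shift from -20% | True reduction needed to read as 30%: 1 - 0.70(1 - r) |
|---|---|---|---|
| 0 | -20.0% | 0 | 30% |
| 0.10 | 0.80/0.90 - 1 = -11.1% | 8.9 points | 37% |
| 0.20 | 0.80/0.80 - 1 = 0.0% | 20.0 points | 44% |
| 0.30 | 0.80/0.70 - 1 = +14.3% | 34.3 points | 51% |

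The mean of a treatment group moves by s times the shift, where s is the share of that group affected. If s were 10%, a true mean of -20% would read as -19.1%, -18.0% or -16.6% for r = 0.10, 0.20 or 0.30. If s were 25%, it would read as -17.8%, -15.0% or -11.4%. With s = 0 nothing changes. The protocol does not give s for either group.

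**The case against.** The strongest reply is that this belongs in the SAP. Section 10.4.3.2 refers the details of secondary analyses there, the SAP is not shown, and it may already separate apheresis subjects. A missing subset table alone would indeed be no finding. But the baseline definition, the changed sampling rule and the endpoints that combine the two are all set by the protocol. The mismatch is in its text whatever the SAP adds.

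Second, no passage states that any enrolled subject is on apheresis or had a Day 1 sample within 2 weeks of a session. Two days is a minimum and an example, not recorded practice. This stands, and the size of the effect is therefore unknown and could be zero.

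Third, no decision depends on it. Part 2 is descriptive, and the bias understates the drug's effect. This also stands and limits the weight of the point.

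Four stronger readings are tempting, and the documents do not support them:
- **The primary result is compromised.** Day 150 was complete before the amendment, and both samples came under the matching instruction. The same holds for the key secondary endpoints.
- **Every apheresis subject is affected.** Those already 2 weeks or more past a session on Day 1 are not.
- **A shift can be quoted for one pooled mean of all subjects.** The summaries are made by treatment group after 2:1 allocation, and where apheresis subjects fall is unknown.
- **The protocol contradicts itself.** The note to criterion 9 assigns its two timings to different periods.

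**Conclusion.** The point holds in a limited form. Where a Day 1 sample was taken less than 2 weeks after a session, change from baseline after local implementation of Amendment 1 compares a baseline that the protocol would itself call confounded with samples that are not. The late open-label reduction is then understated, and the 30% threshold becomes harder to reach.

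The dates follow from the protocol. The direction assumes that a recent session lowers the Day 1 value. The size rests on two quantities that the protocol does not give: the number of affected subjects in each group and the drop in LDL-C per session. The per-subject figures are illustrations over an assumed range. A reader of the planned displays might take a late rise as waning of effect; the displays as planned could not tell the two apart.

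**What to change.** Keep the amended apheresis and sampling rules. Add to Section 10.4.3.2 a statement to this effect:

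> For visits after Day 330, summaries by treatment group of change from baseline in LDL-C, total cholesterol, non-HDL-C and Apo-B, and of LDL-C reduction of at least 30%, will be shown for all subjects and again excluding subjects on apheresis. Where session dates are recorded, the second summary will instead exclude only values whose gap since the last session differs from that at Day 1. A footnote will state that baseline was sampled under the original apheresis timing.

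The documented regimen in criterion 9 identifies the subjects concerned. The second option is the more targeted one, since it keeps apheresis subjects whose gap did not change, but it depends on session dates being available.

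The cost is a short addition to the text and an extra column or figure for each summary. It needs no new visit, sample or change to a session. The second summary will have fewer subjects. If all apheresis subjects are dropped, a difference between the two summaries may partly reflect a different population, so it should not be read as a pure estimate of the artefact.
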